## 5 STUDY TREATMENT

### 5.1 Investigational Product

#### 5.1.1 Investigational Product Supply

Fruquintinib will be supplied by Hutchison MediPharma Limited.

#### 5.1.2 Drug Formulation and Specification

Hutchison MediPharma Limited authorizes WuXi AppTec (Shanghai) Co. Ltd to manufacture and package fruquintinib capsules. The technical guidance and quality assurance will be conducted by Hutchison MediPharma Limited.

**Table 6 Drug Formulation and Strength**

Formulation	Strength	Route of Administration
Capsule	1 mg	Oral
Capsule	5 mg	Oral

#### 5.1.3 Packaging and Drug Labeling

The investigational drug is packaged in white high-density polyethylene bottle with 30 capsules of 1 mg per bottle and 25 capsules of 5 mg per bottle.

The following information will appear on the label affixed to either the bottle or carton; additional information will be added as required:

- Sponsor identification
- Protocol number
- Drug identification
- Quantity of contents
- Storage conditions
- Dosing instructions
- Route of administration
- Blank spaces to write the patient's identification number
- Lot number

#### 5.1.4 Drug Storage

All study drugs should be kept in a secure place under appropriate storage conditions (10°C to 30°C). The investigational product label on the pack specifies the appropriate storage. Fruquintinib capsule should not be used beyond expiration date provided by the manufacturer. The intended shelf life of fruquintinib capsules is 2 years.

The temperature log should be recorded and filed in the study binder.

### 5.1.5 Drug Accountability

All study drug required for this study will be provided by Hutchison MediPharma. The recipient will acknowledge receipt of the drug by returning the appropriate documentation form indicating shipment content and condition. Damaged supplies will be replaced.

Accurate records of all study drug received at, dispensed from, returned to and disposed of by the study site should be recorded by using the Drug Inventory Log.

Study drug will be disposed of at the study site according to the study site's institutional standard operating procedure or returned to Hutchison MediPharma or a Hutchison identified entity with appropriate documentation, as determined by the study site. If the study site chooses to destroy study drug, the method of destruction must be documented.

### 5.1.6 Dose and Administration

After the SRC review of Cohort 2, the RP2D was declared as 5 mg QD, 3 weeks on/1 weeks off each 28-day cycle. Patients from Cohort 1 who remain in the study may have their fruquintinib dose escalated to 5 mg QD at the discretion of the investigator and with the agreement of the Sponsor.

If baseline (pre-dose) PK blood samples need to be collected on the days of PK sample collection, patients must take the investigational product after sampling at site.

It is recommended that fruquintinib be taken with water (approximately 200 mL or 1 cup), 1 hour before breakfast. The administration time should be accurately recorded on the days of PK sampling.

On the days of PK sampling, patients should avoid high-fat meals for the entire day and avoid consumption of any liquids other than water (up to 200 mL) within 1 hour before or after drug administration. The patient is encouraged to avoid, or minimize the use of caffeine-containing foods or drinks, tobacco, tobacco products, and alcohol during the entire study. If the patient cannot avoid taking any of the above listed substances during the study, it should be regarded as a habit and documented as demographic data.

The following substances are **prohibited** during the study: grapefruit or grapefruit juice, illegal drug use, or excessive (> 1 drink/day) alcohol use.

If patients miss a dose in the morning, a replacement dose can be taken before 6 pm on the same day. Otherwise, the patient should not make up the missed dose, but should resume scheduled doses the next day per protocol. The missed dose should be reported to the investigators and recorded in the CRF.

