### 8.1 Analysis Populations

The following analysis populations are defined for the study:

- Safety Analysis Set (SAS): This population includes all patients who have received at least one dose of fruquintinib. Safety data will be evaluated based on this population's outcome. Patients in the SAS will be analyzed by their actual dose initially received. If patients have dose reduction during the study, all data will be summarized/analyzed based on the initial dose of study drug received.
- Pharmacokinetic Analysis Set (PKAS): This population will include all patients who received at least one dose of fruquintinib and have at least 1 PK sample obtained and analyzed.
- Efficacy Analysis Set (EAS): This population includes all patients who have received at least 1 dose of fruquintinib and have at least 1 post-baseline tumor assessment. All efficacy endpoints will be analyzed based on this analysis set.

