15.1. EXPOSURE TO STUDY MEDICATION

Below variables will be summarized:

- Number of cycle(s) received: the number of cycles in which at least one dose of Fruquintinib or placebo is taken. The number of cycles could be further categorized into:
 - 1, 2, 3, 4, 5, 6 and > 6
- Total duration of exposure (days)
- Cumulative dose (mg)
- Dose intensity (mg/day)
- Relative dose intensity (RDI, %): both continuous variable and categorical variable (< 50%; 50 - < 70%; 70 - < 90%; 90 - < 110%; ≥ 110%)
- Actual duration of study treatment (days)
- Percentage intended dose (PID)
- Number of patients with any dose modification (including both drug interruption, dose increase, and dose reduction)
- Frequency of dose modification: 0, 1, 2, 3, 4, 5, 6, >6
- Number of patients experienced drug interruption
- Frequency of drug interruptions: 0, 1, ≥ 2
- Number of patients with any dose reduction
- Reduction from 5mg to 4mg
- Reduction from 4mg to 3mg
- Frequency of dose reduction: 0, 1, 2

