15.2. STUDY MEDICATION COMPLIANCE

The study medication compliance is quantified with relative dose (RD, %) of study medication. RD is calculated as the cumulative dose taken divided by the planned total dose in the corresponding period, expressed as a percentage, see [section 15.3](#) for more details. RDI (%) and RD (%) will be categorized as stated above in [Section 15.1](#).

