15.3. DERIVATIONS

- Total duration of exposure (days) is calculated from the first dose date of study drug in Cycle 1 to the last dose date of study drug + 8 days or death date, whichever comes earlier if treatment is discontinued, or to the cut-off date. if treatment is still ongoing.
- Actual duration of exposure (days) = Sum of the days with study drug administered

Algorithms for calculating parameters relevant to the dose exposure and intensity are listed in Table below:

Document:	[REDACTED]		
Author:	[REDACTED]	Version Number:	2.5
		Version Date:	18Feb2022
Template No.:	[REDACTED]	Reference:	CS_WI_BS005
Effective Date:	02Dec2019		

Parameter	Description/ Formula [a]
Dosing schedule per protocol#	5 mg PO QD between Days 1 and Day 21, followed by 1-week off
Cumulative dose (mg) [b]	$\sum [5 \times (\text{all dispensed 5-mg tablets} - \text{total returned 5-mg tablets} - \text{total lost 5-mg tablets in a cycle}) + 1 \times (\text{all dispensed 1-mg tablets} - \text{total returned 1-mg tablets} - \text{total lost 1-mg tablets in a cycle})]$
Dose intensity (mg/day)	Cumulative dose (mg) / Total duration of exposure (day)
Relative dose intensity (RDI, %) #	$100 * [\text{Dose intensity (mg/day)} / (5 \times 21/28, \text{mg/day})]$
Relative Dose (RD, %) #	$100 * [\text{Cumulative dose (mg)} / (5 \times 21 \times \text{number of cycles received (mg)})]$
Percentage intended dose (PID, %) [c]	$100 * [(\text{total number of days with any recorded doses}) / \text{total duration of exposure (days)}]$

[a]In the study, there are the other dose level of "3mg QD" used.

[b]In the study, both 1-mg and 5-mg fruquintinib are provided for oral administration. When dose adjustment is required, 1-mg fruquintinib is always used. Before calculating the cumulative dose, total number of 1-mg and 5-mg tablets taken should be counted separately.

[c]Given the dose schedule of a 4-week cycle in the protocol, 3 weeks on/ 1 week off, the reference value is 0.75.

indicates 5 (mg) should be replaced with 3 (mg) for calculation in Cohort "3 mg QD".

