APPENDIX 2. PROGRAMMING CONVENTIONS FOR OUTPUTS

Output Conventions

For more details please refer to the general rules listed in the shell.

Dates & Times

Depending on data available, dates and times will take the form ddmmyyyyThh:mm:ss.

Spelling Format

English US.

Presentation of Treatment Groups

For outputs, treatment groups will be represented as follows and in that order:

Treatment Group	For Tables
Dose Escalation Phase: 3mg QD	Dose Escalation Phase: Fruquintinib 3mg QD
Dose Escalation Phase: 5mg QD	Dose Escalation Phase: Fruquintinib 5mg QD
Dose Expansion Phase (5mg QD): Cohort A	Dose Expansion Phase: Cohort A
Dose Escalation Phase: 5mg QD + Dose Expansion Phase (5mg QD): Cohort A	Dose Expansion Phase: Dose Escalation Fruquintinib 5mg QD + Cohort A
Dose Escalation Phase + Dose Expansion Phase	Dose Expansion Phase: Dose Escalation Phase + Dose Expansion Phase (Only for Patient Disposition, Demographic and Baseline Characteristics, Baseline Cancer Characteristics tables)

Treatment Group	For Listings
Dose Escalation Phase: 3mg QD	Dose Escalation Phase: Fruquintinib 3mg QD
Dose Escalation Phase: 5mg QD	Dose Escalation Phase: Fruquintinib 5mg QD
Dose Expansion Phase (5mg QD): Cohort A	Dose Expansion Phase: Cohort A

Treatment Group	For Figures
Dose Escalation Phase: 3mg QD	Dose Escalation Phase: Fruquintinib 3mg QD
Dose Escalation Phase: 5mg QD	Dose Escalation Phase: Fruquintinib 5mg QD

Document: [REDACTED]

Author: [REDACTED]

Version Number:

2.5

Version Date:

18Feb2022

Template No.: [REDACTED]

Reference: CS_WI_BS005

Effective Date: 02Dec2019

Treatment Group	For Figures
Dose Expansion Phase (5mg QD): Cohort A	Dose Expansion Phase: Cohort A
Dose Escalation Phase: 5mg QD and Dose Expansion Phase (5mg QD): Cohort A	Pooling Dose Escalation 5 mg and Cohort A
Dose Escalation Phase: 3mg QD + Dose Escalation Phase: 5mg QD and Dose Expansion Phase (5mg QD): Cohort A	Dose Escalation 3mg and Pooling Dose Escalation 5mg and Cohort A

Presentation of Visits

For outputs, visits will be represented as follows and in that order:

Long Name (default)	Short Name
Baseline	Baseline
Cycle 1 Day 1	C1D1
Cycle 1 Day 8	C1D8
Cycle 1 Day 15	C1D15
Cycle 1 Day 22	C1D22
Cycle 2 Day 1	C2D1
Cycle 2 Day 15	C2D15
Cycle 3 Day 1	C3D15
Cycle 4 Day 1	C4D1
Cycle X Day 1	CXD1
.....
End of Treatment	EOT

Listings

All listings will be ordered by the following (unless otherwise indicated in the template):

Assigned treatment group, unless otherwise specified

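### SAP 15.3 keeps 3 mg as the RD and RDI reference for Cohort 1 patients escalated to 5 mg, so both measures overstate their compliance

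*Protocol*

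**What the plan says.** Protocol 5.1.6 declares 5 mg QD, three weeks on and one week off, as the RP2D. It then says that "Patients from Cohort 1 who remain in the study may have their fruquintinib dose escalated to 5 mg QD", at the investigator's discretion and with the sponsor's agreement.

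SAP 15.2 states: "The study medication compliance is quantified with relative dose (RD, %) of study medication". It adds that "RD is calculated as the cumulative dose taken divided by the planned total dose in the corresponding period" and refers to SAP 15.3 for detail. The SAP 15.3 table divides cumulative dose by 5 × 21 × cycles received for RD, and divides dose intensity by 5 × 21/28 for RDI. A footnote to both "indicates 5 (mg) should be replaced with 3 (mg) for calculation in Cohort" 3 mg QD. No rule covers a patient whose dose goes up.

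Escalated patients stay in that cohort. Protocol 8.1 says "Patients in the SAS will be analyzed by their actual dose initially received", and SAP 4.2 repeats it. SAP 15.1 bands RDI as <50%, 50 to <70%, 70 to <90%, 90 to <110% and ≥110%; SAP 15.2 applies the same bands to RD.

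**The concern.** Once a sponsor-agreed escalation has taken place, 3 mg is no longer the dose the patient is meant to take. A ratio that still divides by 3 mg does not measure compliance. It can put a patient in the wrong band in either direction: a fully compliant patient appears in the ≥110% band, and a clearly under-dosed one appears in the 90 to <110% band. What is at stake is the accuracy of the named compliance measure for these few patients.

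**Working it through.** **Inputs.** 21 dosing days per 28-day cycle (SAP 15 and 15.3), so a full cycle is 3 × 21 = 63 mg or 5 × 21 = 105 mg. The schedule basis reproduces the SAP's own figure: 21/28 = 0.75, the reference value given for percentage intended dose (PID). The documents do not say how many patients escalated or when, so the splits below are illustrative assumptions.

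**Full compliance.** With k cycles at 3 mg and m at 5 mg, the SAP 15.3 formula gives RD = (63k + 105m) / [63(k + m)].

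| Cycles at 3 mg + 5 mg | Taken (mg) | SAP denominator (mg) | RD |
|---|---|---|---|
| 2 + 1 | 231 | 189 | 122.2% |
| 4 + 1 | 357 | 315 | 113.3% |
| 6 + 1 | 483 | 441 | 109.5% |
| 2 + 4 | 546 | 378 | 144.4% |

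If f is the share of cycles at 5 mg, RD = 1 + (2/3)f. The ≥110% band is reached when f ≥ 0.10/(2/3) = 0.15. The 6 + 1 split has f = 1/7 = 0.143 and falls just short.

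RDI behaves in the same way over whole cycles. For 2 + 1, (231/84) / (3 × 21/28) = 2.75/2.25 = 122.2%. If the duration is counted inclusively as 85 days, it is 120.8%.

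**Missed 5 mg doses.** Let x be the fraction of 5 mg doses missed, with no 3 mg dose missed. RD = 100% when 63k + 105m(1 − x) = 63(k + m), so 1 − x = 63/105 = 0.60 and x = 40% for any k and m. The figure depends on full 3 mg compliance. With 4 + 4 cycles and a fraction g of 3 mg doses missed, x = 1 − [24 − 12(1 − g)]/20, which is 34% at g = 10% and 28% at g = 20%.

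**Band example.** Take 2 + 1 cycles with 8 of the 21 doses at 5 mg missed, and the last scheduled dose taken.
- Dose taken: 126 + 13 × 5 = 191 mg.
- SAP 15.3: 191/189 = 101.1%, band 90 to <110%.
- Planned dose: 191/231 = 82.7%, band 70 to <90%.
- PID: (42 + 13)/84 = 65.5%, against a reference of 75%.

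**After the correction.** The denominator becomes 63k + 105m. Full compliance then gives 100% for every split. For 4 + 4 cycles with 40% of 5 mg doses missed, RD is (252 + 252)/(252 + 420) = 75.0%, where the present formula gives 100%.

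**The case against.** The strongest defence is that the opening of SAP 15 ties planned treatment to the cohort (3 mg or 5 mg QD), and SAP 15.2 defers to SAP 15.3. On that reading the 3 mg denominator follows the SAP's meaning of planned dose and matches analysis by initial dose. This softens the conflict between the two sections. It does not make RD a valid compliance measure for someone instructed to take 5 mg.

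A second argument is consistency. A 5 mg starter reduced to 4 mg who takes every dose reads 4/5 = 80%, because the denominator stays put, so the same should apply upwards. The cases differ: a toxicity reduction is a shortfall from the plan, whereas an agreed escalation changes the plan.

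Third, SAP 15.1 has a ≥110% band and counts dose increases as modifications, so high values are foreseen. That is true, but the band cannot separate a compliant escalated patient from one who took too much.

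Fourth, missed doses are visible elsewhere. PID counts the "total number of days with any recorded doses", and interruptions and cumulative dose are also summarised. This stands and limits the harm. It does not correct the measure the SAP names for compliance.

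A reader might also infer that adverse events after escalation have no defined place. The documents do not support that. They fall within the TEAE window of SAP 17.2, and the initial-dose rule puts them under "Dose Escalation Phase: Fruquintinib 3mg QD". Their timing can be rebuilt from listings: SAP 17.2 lists all AEs, SAP 5.1 adds study day, and Protocol 8.2 flags dose modifications. Appendix 2 shows no separate group for them, but it also omits Cohorts B to E and refers to shells not available here, so it is not a complete list of outputs.

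Nor does Protocol Table 7 leave escalated patients without any rule. It is keyed to starting dose. The 3 mg column fits poorly, since its only step is 3 to 2 mg, but the only ladder containing 5 mg is 5 to 4 to 3. Investigator and sponsor would be expected to settle on it.

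**Conclusion.** The concern holds for the RD and RDI denominator. For any Cohort 1 patient escalated to 5 mg, SAP 15.3 gives a value above 100% at full compliance and can raise an under-dosed patient by a band. The formulas are exact; the sizes depend on the assumed switch time, and the 40% threshold depends on no 3 mg dose being missed.

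The effect is minor. The 3 mg cohort was planned at six DLT-evaluable patients (Protocol 3.1.1) and only those still on study could escalate, so between none and about six are affected. If nobody escalated, no output changes. Only descriptive exposure and compliance tables are involved: PID, DLT incidence, the RP2D and PFS do not use this denominator. The correction is still worth making, because a stated rule gives a wrong number and putting it right costs almost nothing.

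**What to change.** Add a note to SAP 15.3 for patients escalated from 3 mg to 5 mg:
- RD denominator = 3 × 21 × (cycles planned at 3 mg) + 5 × 21 × (cycles planned at 5 mg), over cycles received.
- RDI reference = that total divided by 28 × all cycles received.
- Split a mid-cycle switch by planned dosing days. A switch after 7 dosing days gives 7 × 3 + 14 × 5 = 91 mg for that cycle.
- Leave the denominator unchanged after a toxicity reduction, as for 5 mg starters.

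This needs a SAP note and limited programming from dosing records already collected, with no protocol change.

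Two clarifications are optional. A flag on AEs that start or worsen on or after the first 5 mg dose would help readers of the 3 mg column; its denominator would be very small, and late events may reflect earlier 3 mg exposure, so it would be descriptive only. A sentence in Protocol Table 7 could say that escalated patients follow the 5 to 4 to 3 mg sequence, for which SAP 15.1 already has rows ("Reduction from 5mg to 4mg", then 4 to 3 mg). As a protocol change it needs IEC/IRB review (Protocol 9.1), so it should wait for another amendment.

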## 5.2 Dose Modification

### 5.2.1 General Dose Adjustment Note

The severity of AEs will be graded according to the NCI CTCAE v4.03. Reasons for dose modifications or delays, the supportive measures taken, and the outcome will be documented in the patient's chart and recorded in the CRF.

- Any toxicity that meets the definition of DLT during the DLT observation period will be considered as DLT for purposes of dose escalation and MTD determination.
- For any concomitant conditions already apparent at baseline, the dose modifications will apply according to the corresponding shift in toxicity grade, if the investigator feels it is appropriate. For example, if a patient has Grade 1 asthenia at baseline that increases to Grade 2 during treatment, this will be considered a shift of one grade and treated as Grade 1 toxicity for dose-modification purposes.
- For toxicities that are considered by the investigator to be unlikely to develop into serious or life-threatening events, treatment will be continued at the same dose. In addition, no dose reductions or interruptions will be required for anemia (non-hemolytic) because it can be satisfactorily managed, unless serious (Grade  $\geq 3$ ) hemorrhage is present.
- To recover from acute toxicity, unless otherwise indicated, the treatment can be interrupted for up to 14 days. If a treatment delay longer than 14 days is required, the patient should be discontinued from the study drug. Continuation/resumption of fruquintinib treatment after an interruption of more than 14 days must be discussed with the medical monitor or his or her designee.
- Where several toxicities with different grades or severity occur at the same time, the dose modifications should be according to the highest grade observed.

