**Table 8 Dose Modification for Hematologic and Non-Hematologic Toxicity**

NCI CTCAE v4.03 Toxicity Grading	Action
Grade 1 or 2 a	None
Grade 3 b	Interrupt the dose until the toxicity resolved to ≤Grade 1 or baseline level within 14 days, then reduce the dose to lower a dose level
Grade 4	Discontinue treatment permanently

a Should any arterial thrombosis occur, the treatment should be terminated.

b Including Grade 3 diarrhea and stomatitis, etc. that are ineffectively treated by drug therapies, but excluding Grade 3 menstrual cycle extension.

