**Table 11 Dose Modification for Hypertension**

AE Grading and Definitions	Dose adjustment	Treatment Suggestions
Grade 1: prehypertension  (systolic BP 120-139 mmHg or diastolic BP 80-89 mmHg)	None	Follow up as planned schedule
Grade 2: SBP 140-159 mmHg or DBP of 90-99 mmHg; or DBP symptomatic increase >20 mmHg	None	Treatment objective: lower the blood pressure to <140/90 mmHg (or <130/80 mmHg in patients with chronic renal disease and/or diabetes).  Refer to Appendix I .
Grade 3: SBP $\geq$ 160 mmHg or DBP $\geq$ 100mmHg; or more than one drug or more intensive therapy are used	Interrupted once Grade3 hypertension lasting more than 7 days after using or adjusting antihypertensive drug; Should the BP of the patient recover to Grade 1 or the baseline level, one time of dose reduction shall be made.	Treatment objective: lower the blood pressure to <140/90 mmHg (or <130/80 mmHg in patients with chronic renal disease and/or diabetes).  Refer to Appendix I .
Grade 4: Life threatening (eg, malignant hypertension, temporary or permanent neurological deficits and hypertensive crisis)	The drug should be terminated.	Emergent medical treatment.

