**Table 12 Dose Adjustment for Decreased Platelet Count**

AE Grading	Dose Adjustment	Treatment Suggestions
Grade 1: Platelet count <LLN - 75,000/ mm  ; <LLN - 75.0 × 10  /L	None	Perform follow up visit as scheduled.
Grade 2: Platelet count <75,000- 50,000/mm  ; <75.0 - 50.0 × 10  /L	Be interrupted and continue the drug treatment with the same dose should the AE recovers to Grade 1 or baseline level within 7 days.	Hematology test should be monitored every 2-3 days; active treatment for platelet elevation is recommended.
	Be interrupted and then reduced to the lower dose level should the AE recovers to Grade 1 or baseline level within 7-14 days.	Hematology test should be monitored every 2-3 days; active treatment for platelet elevation is recommended.
Grade 3: Platelet count <50,000 - 25,000/mm  ; <50.0 - 25.0 × 10  /L	Be interrupted and reduced to the lower dose level should the AE recovered to Grade 1 or baseline level within 14 days.	Hematology test should be monitored every 2-3 days; active treatment (platelet transfusion) to elevate the platelet count is recommended.  Hematology examination should be performed once every week in the follow up visit.
Grade 4: Platelet count <25,000/mm  ; <25.0 × 10  /L	The study drug should be terminated permanently.	Hematology test should be performed once daily until the AE recovers to Grade 2 or a lower grade; platelet transfusion or other active treatment should be provided

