**Table 13 Dose Adjustment for Hemorrhage at any Site**

AE Grading	Dose Adjustment	Treatment Suggestions
Grade 1	None	Perform follow up visit as scheduled.
Grade 2	The drug can be interrupted and then reduced to the lower dose level should the AE recovered to Grade 1 or baseline level within 14 days.	Provide Active treatment b
Grade 3 or abovea	The study drug should be terminated permanently.	Emergent medical intervention b

a Refer to [Appendix J](#) for clinical management of severe or serious hemorrhage.

b The investigator should closely monitor patients receiving anti-platelet and/or anti-thrombotic drugs during study drug treatment and make a timely decision on whether to continue or stop such drugs in patients that report Grade ≥2 hemorrhagic events at any site, based on an individual assessment of the risk-benefit balance (See Section 5.3.1 Concomitant therapies).

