**Table 14 Dose Adjustment for Abnormal Liver Function**

AE Grading a	Dose Adjustment	Treatment Suggestions
Grade 1	None.	Perform follow-up visit as scheduled.
Grade 2 or 3 (Liver function is abnormal but the biochemical criteria for Hy's Law b are not met)	
 
1. Drug interruption can be considered;
 
2. The dose should be reduced to the lower dose level if the AE recovers to Grade 1 or baseline within 14 days.
 
	Provide supportive care and increase the frequency of liver function monitoring to 1-2 times a week.
Grade 2 or 3 (Liver function is abnormal and the biochemical criteria for Hy's Law b are met)	The study drug should be terminated immediately.	Provide supportive care and increase the frequency of liver function monitoring to 2-3 times a week. Urgent medical intervention indicated.
Grade 4	The study drug should be terminated.	Urgent medical intervention indicated.

a Including increasing of ALT, AST, and total bilirubin, whether or not the biochemical criteria for Hy's Law have been met.

b Hy's Law is an increase in serum AST or ALT  $\geq 3 \times$  ULN together with total bilirubin  $\geq 2 \times$  ULN, and no other reason can be found to explain the biochemical changes, for example, new or worsening hepatobiliary metastases, elevated serum ALP indicating cholestasis, viral hepatitis, another suspect drug, or any other specific cause of severe hepatocellular injury. The elevation in transaminases must precede or be coincident with (ie, on the same day as) the elevation in total bilirubin, but there is no specified timeframe within which the elevations in transaminases and total bilirubin must occur. See Section 7.1.2 for special reporting requirements and Appendix H for additional information regarding Hy's Law.

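### The optional shift-from-baseline rule in Protocol Section 5.2.1 has no upper grade, so a Grade 4 event from a Grade 1 baseline can be managed under a Grade 3 row instead of a permanent stop

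*Protocol*

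**What the plan says.** The second bullet of Section 5.2.1 concerns concomitant conditions already apparent at baseline. For these, "the dose modifications will apply according to the corresponding shift in toxicity grade, if the investigator feels it is appropriate". Its only example is asthenia: Grade 1 at baseline rising to Grade 2 on treatment is handled as Grade 1. The bullet names no highest grade to which it applies and does not say that mandatory stops take precedence.

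Five tables stop the drug at a fixed grade:

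- Table 8 (general toxicity), Grade 4: "Discontinue treatment permanently". At Grade 3 the drug is interrupted until recovery within 14 days, "then reduce the dose to lower a dose level".
- Table 11 (hypertension), Grade 4: "The drug should be terminated".
- Table 12 (platelets), Grade 4: "The study drug should be terminated permanently".
- Table 13 (hemorrhage), Grade 3 or above: permanent termination. At Grade 2: "The drug can be interrupted and then reduced to the lower dose level should the AE recovered" to Grade 1 or baseline within 14 days.
- Table 14 (liver function), Grade 4: "The study drug should be terminated". Grade 2 or 3 also stops if the Hy's Law criteria are met.

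Tables 9 and 10 (PPE and proteinuria) stop on recurrence rather than at a fixed grade, so they are not part of this point.

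The fourth bullet of Section 5.2.1 adds a general limit: "If a treatment delay longer than 14 days is required, the patient should be discontinued from the study drug". Continuing after a longer gap must be discussed with the medical monitor.

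**The concern.** The shift rule does not compete with the tables. It decides which row of a table is used. If the row is chosen by the change from baseline, a patient who enters with a mild abnormality is one grade further from a mandatory stop than a patient who enters with none, even when both have the same Grade 4 event.

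These stops are the strictest dose actions in the protocol. Whether they apply should not turn on a Grade 1 finding at entry. As worded, two sites could each follow the protocol after the same Grade 4 event, one terminating and the other interrupting and resuming at a lower dose. What is at stake is patient safety and consistent management.

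**Working it through.** **Step 1. The rule as a formula.** Grade used for dosing = observed grade − baseline grade. The plan's own example is reproduced: 2 − 1 = 1.

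**Step 2. Apply it to the stops, with the same condition at Grade 1 at baseline.**

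| Table | Observed grade that stops the drug | Grade after shift | Action in the row then used |
|---|---|---|---|
| 8 | 4 | 4 − 1 = 3 | Interrupt; reduce after recovery within 14 days |
| 11 | 4 | 4 − 1 = 3 | Interrupt only if Grade 3 persists beyond 7 days on new or adjusted antihypertensives; one reduction after recovery |
| 12 | 4 | 4 − 1 = 3 | Interrupt; reduce after recovery within 14 days |
| 14, Hy's Law not met | 4 | 4 − 1 = 3 | Interruption optional; reduce after recovery within 14 days |
| 13 | 3 | 3 − 1 = 2 | May interrupt; reduce after recovery within 14 days |
| 13 | 4 | 4 − 1 = 3 | Still in the Grade 3 or above row: terminate |

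With baseline Grade 0 the shifted grade equals the observed grade and every stop stands.

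**Step 3. Can an eligible patient have the Grade 1 baseline?**

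- Table 8: yes. Exclusion 24 bars unresolved toxicity of earlier antitumor treatment only above Grade 1.
- Table 11: yes. Grade 1 is 120–139 mmHg systolic or 80–89 mmHg diastolic, and exclusion 8 starts at 140/90.
- Table 14: yes. Exclusion 4 allows ALT/AST up to 1.5 x ULN, or 3 x ULN with liver metastases. Exclusion 3 allows bilirubin up to 1.5 x ULN. In SAP Appendix 6, values above ULN and up to 3 x ULN (ALT/AST) or 1.5 x ULN (bilirubin) are Grade 1.
- Table 12: only under an assumption. Exclusion 2 requires platelets of at least 100 x 10^9/L and Grade 1 begins below the local lower limit of normal, so that limit must exceed 100 x 10^9/L. The documents do not give it.
- Table 13: rarely. Exclusion 10 bars active gastrointestinal bleeding and conditions that risk it within 6 months of screening; exclusion 11 bars bleeding from other sites within 2 months. What remains is a narrow gap, such as a bleed that starts during screening. Appendix J then still requires at least immediate interruption at Grade 3 or above.

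**Step 4. How large are the events?** Grade 4 limits are from SAP Appendix 6; entry values are at the eligibility limit.

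- ALT/AST above 20 x ULN: more than 20/3 = 6.7 times entry with liver metastases, or 20/1.5 = 13.3 times without.
- Bilirubin above 10 x ULN: more than 10/1.5 = 6.7 times entry.
- Platelets below 25 x 10^9/L: a fall of more than (100 − 25)/100 = 75% from 100 x 10^9/L.

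These figures show that the events are not drift around an abnormal baseline. They do not measure how often such events occur.

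**Step 5. Stops that the shift cannot displace.** The Hy's Law stop is set by multiples of ULN and is separately mandatory in Section 7.1.3.2 and Appendix H. The arterial thrombosis stop (Table 8 footnote a, Section 5.3.1) does not depend on grade.

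**The case against.** The best case against is that ordinary reading already settles the matter. Section 5.2.1 is a general note. Tables 9 to 14 give specific instructions for selected risks, and some Grade 4 rows are stated as absolute findings, such as a platelet count. The shift rule is optional, and its one example is a minor change in asthenia. Calling a hypertensive crisis a shift from prehypertension strains the wording.

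There are also safeguards. The substitute rows in Tables 8, 12, 13 and 14 require recovery to Grade 1 or baseline within 14 days before a reduced dose. The 14-day stop and the intolerable-toxicity stop still apply. Life-threatening events and Grade 3 or above hemorrhages reach the sponsor within 24 hours, although an isolated Grade 4 laboratory value may not qualify as serious. Appendix I records no Grade 4 hypertension to date.

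Most of this stands, and it limits frequency and consequence. It does not close the gap. Saying that the specific table controls does not help when the general note supplies the grade with which the table is entered. The bullet on several simultaneous toxicities, which uses the highest grade, does not cap the shift either.

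A reader might infer that every permanent stop in Tables 8 and 11 to 14 can be set aside. The documents do not support that: the Hy's Law stop, the arterial thrombosis stop and Grade 4 hemorrhage from a Grade 1 baseline survive, Table 13 is barely reachable at Grade 3, and Table 12 is conditional.

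A reader might also subtract a Grade 2 or 3 baseline and reach no action at all, for example by grading hypertension controlled on two drugs as Grade 3. The arithmetic allows it, but the documents do not say how a controlled patient is graded at baseline. Eligibility also holds ALT/AST, bilirubin, platelets and residual treatment toxicity to Grade 1 at most. The point does not rest on that case.

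**Conclusion.** The concern holds in a limited form. When the same condition was present at Grade 1 at baseline, the wording allows a Grade 4 event to be managed under the Grade 3 row. That is so for Tables 8 and 11, for Table 14 when Hy's Law is not met, and for Table 12 if the local platelet limit exceeds 100 x 10^9/L. The Grade 3 hemorrhage stop in Table 13 is exposed only in a rare gap.

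The conclusion assumes that an investigator elects to use the rule and reads it literally. The number of patients affected cannot be derived: the documents give no distribution of baseline grades, and the on-treatment risk frequencies in Protocol Table 3 do not supply one.

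A reader might infer that the trial's results are at risk. Nothing in the documents supports that. The rule is confined to dose modification, the first bullet of Section 5.2.1 keeps DLT classification separate, and the SAP grades adverse events and laboratory values by CTCAE rather than by this shift. This is a low-frequency patient-safety point that should be corrected because the consequence is serious and the correction is small.

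**What to change.** In Section 5.2.1, second bullet, after the asthenia example, add:

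> This shift rule does not apply to any event for which Tables 8 and 11 to 14 require discontinuation of study drug at the observed CTCAE grade (Grade 4 events; Grade 3 or above hemorrhage); the observed grade then applies.

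Leave shift grading at lower grades as it is. No table, data collection or analysis changes; sites need a short notice.

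The cost is slightly less investigator discretion and possibly a few more discontinuations, for example for Grade 4 laboratory values such as lymphocytes or triglycerides in patients whose baseline was already abnormal. If the sponsor wants baseline-adjusted judgment for particular laboratory values, it should name them as exceptions in the same bullet.
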